~~Subjects who withdraw are to be followed for radiologic progression as outlined in Section 6.4.2. In addition~~ **Following subject withdrawal**, every effort will be made to collect safety information on each subject through 30 days following the last dose of study treatment, unless the subject withdraws consent and refuses to comply with the protocol stipulated safety follow-up ~~and radiologic disease progression assessments~~, or share information obtained after the date of withdrawal of consent.

Section 6.6 Withdrawal of Subjects from Study, paragraph 2

Formerly:

Every effort will be made to collect follow-up information on subjects in the long-term follow-up period of the study, unless the subject withdraws consent and refuses to share information obtained during the long-term follow-up period obtained after the date of withdrawal of consent.

Deleted

Section 6.7 Disease Response Assessments

Modified to:

Section 6.8 Disease Response Assessments

Added:

Section 6.8.1. Disease Response Assessments for Subjects in the Extended Access Phase

During the Extended Access phase, subjects will have regular visits for disease assessments at least every 3 months or as per standard of care, whichever is sooner, until disease progression is documented. Independent radiological review for confirmation of disease progression is not required.

Section 6.9 Treatment after the end of the Study

The investigator is responsible for ensuring that consideration has been given to the post-study care of the subject's medical condition, whether or not GSK is providing specific post-study treatment

Section 8.2 Reporting Adverse Events to the Sponsor or Designee

Added:

The investigator and their designees are responsible for detecting, documenting and reporting events that meet the definition of an AE or SAE.

Any SAEs assessed as related to study participation (e.g., protocol-mandated procedures, invasive tests, or change in existing therapy) or related to a Human Genome Science product will be recorded from the time a subject consents to participate in the study up to and including any follow-up contact.

Investigators are not obligated to actively seek AEs or SAEs in former study subjects. However, if the investigator learns of any SAE, including a death, at any time after a subject has been discharged from the study, and he/she considers the event reasonably related to the study treatment or study participation, the investigator must promptly notify GSK CMG.

Formerly:

Serious Adverse Events (SAEs) must ALSO be recorded on the SAE Worksheet and sent to HGS within 24 hours of site personnel becoming aware of a SAE, regardless of expectedness. All pages of the SAE Worksheet will be completed, but the SAE worksheet will not be held until all information is available. Additional information and corrections will be provided on subsequent SAE Worksheets as described in the Study Procedure Manual. SAE Worksheets

will be sent by facsimile to the Drug Safety Department at HGS using the fax number listed below.

FAX #: PPD

Modified to:

Serious Adverse Events (SAEs) must ALSO be recorded on the SAE Worksheet and ~~sent to HGS emailed to GSK CMG at PPD (fax backup: PPD)~~ within 24 hours of site personnel becoming aware of a SAE, regardless of expectedness. All pages of the SAE Worksheet will be completed, but the SAE worksheet will not be held until all information is available. Additional information and corrections will be provided on subsequent SAE Worksheets as described in the Study Procedure Manual. ~~SAE Worksheets will be sent by facsimile to the Drug Safety Department at HGS using the fax number listed below.~~

FAX #: PPD

Section 8.8 Serious Adverse Events Assessed During Long-term Follow-up

Formerly:

SAEs that occur after the safety follow-up period (30 days following the final dose of study agent) that are assessed by the investigator as possibly, probably, or definitely related to study agent must be reported to Human Genome Sciences on an SAE worksheet, as described in Section 8.2. Post-study SAEs will not be documented on the AE case report form.

Deleted.

Section 8.8 Serious Adverse Events Assessed During Long-Term Follow-up

Section Deleted.

Added:

Section 8.8 Regulatory Reporting Requirements for SAEs

Prompt notification by the investigator to Human Genome Science of SAEs and non-serious AEs related to study treatment (even for non-interventional post-marketing studies) is essential so that legal obligations and ethical responsibilities towards the safety of subjects and the safety of a product under clinical investigation are met.

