Appendix 8 Treatment of Allergic/Hypersensitivity Reactions

In the event of allergic/hypersensitivity reactions to mapatumumab/placebo, investigators will institute treatment measures according to best medical and nursing practice. The grading is based upon the NCI-CTCAE Version 4.0.0.

The following treatment guidelines will be employed:

- If chills and fever occur, the infusion will be interrupted. Subjects may be treated symptomatically and the infusion will be restarted at 50% of the original rate.

Grade 1 allergic/hypersensitivity reaction (transient flushing or rash, drug fever < 38°C):

- Decrease infusion rate by 50% and monitor for worsening condition. If the reaction worsens, stop the infusion.

Grade 2 allergic/hypersensitivity reaction (rash, flushing, urticaria, dyspnea, drug fever < 38°C):

- Stop the infusion.
- Administer bronchodilators, oxygen, acetaminophen, etc as medically indicated.
- Resume infusion at 50% of previous rate once reaction has decreased to ≤ Grade 1 in severity. Monitor closely for any worsening. If the reaction recurs, stop the infusion.

Re-treatment following Grade 1 or Grade 2 allergic/hypersensitivity reactions:

- Once the infusion rate has been decreased due to an allergic/hypersensitivity reaction, it will remain decreased for all subsequent infusions.
- If the subject has a 2nd reaction at the lower infusion rate, the infusion will be stopped and the subject will receive no further treatment with mapatumumab/placebo.
- If the subject experiences a Grade 3 or Grade 4 allergic/hypersensitivity reaction at any time, the subject will receive no further treatment with mapatumumab/placebo.
- If there are questions concerning whether an observed reaction is an allergic/hypersensitivity of Grades 1-4, the medical monitor will be contacted immediately to assist with grading the reaction.

Grade 3 or Grade 4 allergic/hypersensitivity reaction:

- A Grade 3 hypersensitivity reaction consists of symptomatic bronchospasm requiring parenteral medications with or without urticaria, allergy-related edema/angioedema, or asymptomatic hypotension not requiring treatment.
- A Grade 4 hypersensitivity reaction (ie, anaphylaxis) is a life-threatening event characterized by the same symptoms as in a Grade 3 reaction but also complicated by symptomatic hypotension or oxygen saturation of 90% or less.

Treatment of Grade 3 or Grade 4 allergic/hypersensitivity reaction:

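### Appendix 8 uses the same fever limit, below 38°C, for Grade 1 and Grade 2 infusion reactions, so an isolated low fever has two different instructions

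*Protocol*

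**What the plan says.** Protocol Appendix 8 bases its grading on NCI-CTCAE 4.0.0 and describes each grade by listing signs.

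- Grade 1 heading: "Grade 1 allergic/hypersensitivity reaction (transient flushing or rash, drug fever < 38°C". Instruction: "Decrease infusion rate by 50% and monitor for worsening condition. If the reaction worsens, stop the infusion".
- Grade 2 heading: "Grade 2 allergic/hypersensitivity reaction (rash, flushing, urticaria, dyspnea, drug fever < 38°C". Instruction: stop the infusion, give supportive treatment, then "Resume infusion at 50% of previous rate once reaction has decreased to ≤ Grade 1 in severity".
- A separate bullet precedes both grades: "If chills and fever occur, the infusion will be interrupted". It needs chills as well as fever and gives no temperature.
- Grade 3 contains no fever term: "A Grade 3 hypersensitivity reaction consists of symptomatic bronchospasm requiring parenteral medications with or without urticaria, allergy-related edema/angioedema, or asymptomatic hypotension not requiring treatment". Grade 4 builds on Grade 3 and also has none.

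The appendix has two general safeguards. It says that "investigators will institute treatment measures according to best medical and nursing practice", and that if the grade is in question "the medical monitor will be contacted immediately to assist with grading the reaction". Protocol Section 5.1.3 plans a constant-rate infusion over 1 hour with close observation. The SAP does not address this point.

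**The concern.** The two headings are meant to route a subject to different actions, but the fever limit is identical in both. Flushing and rash also appear in both lists, but there Grade 1 is marked as transient. Fever carries no such qualifier. A nurse who sees an isolated drug fever below 38°C can follow the printed text to either instruction.

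The restart rule has the same weakness. A Grade 2 infusion may resume once the reaction is Grade 1 or lower, and an isolated fever below 38°C already meets the Grade 1 description at the moment the infusion is stopped.

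Fever is a plausible event here. Protocol Section 1.4.3 names pyrexia among the most frequent treatment-related events, seen in more than 10% of subjects on single-agent mapatumumab. It does not say when the pyrexia occurred relative to the infusion, so that figure is not a rate of affected infusions.

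**Working it through.** No power, sample size or alpha figure is involved. The check is a comparison of the text, with one short calculation to bound the effect.

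**Which rule applies to a fever with no other listed sign (Appendix 8)**

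| Situation | Grade 1 heading | Grade 2 heading | Instruction |
|---|---|---|---|
| Below 38°C, no chills | met | met | two: halve the rate, or stop, treat and resume at half rate |
| Starts below 38°C, then rises | met at onset | met at onset | on the Grade 1 path, stop because the reaction has worsened |
| First recorded at 38°C or more, no chills | not met | not met | none listed |
| Any fever with chills | – | – | interrupt, then restart at half the starting rate |

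The first row is the conflict. The third row is a gap, but a narrow one, because the second and fourth rows cover the neighbouring cases.

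**Is it a text-reading fault?** The Grade 1 and Grade 2 headings are the same in all four protocol versions: the original and Amendments 01, 02 and 03. The symbol ≤ is printed correctly in the same appendix. A conversion error is therefore unlikely. The Amendment 03 revision chronology dates the versions from 14 September 2010 to 15 July 2015, which is 1,765 days (1,765 / 365.25 = 4.8 years). That is the age of the wording and does not measure harm.

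**How different are the two paths?** Take the planned 60-minute infusion with one reaction at minute *t* and half rate afterwards. The running time is

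*t* + 2 × (60 − *t*) = 120 − *t* minutes.

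| *t* (min) | Running time (min) |
|---|---|
| 0 | 120 |
| 30 | 90 |
| 60 | 60 |

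This is the same on both paths. The Grade 2 path adds a stop of *s* minutes, giving 120 − *t* + *s*. The appendix does not state *s*, so the direct difference per infusion is *s* and cannot be put in numbers from the documents.

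**One indirect route (inference).** A second reaction at the reduced rate ends mapatumumab/placebo for that subject. On the Grade 2 path, a fever that settles during the stop and returns at half rate could be counted as a second reaction. On the Grade 1 path, the same fever continuing without a break might not be. The documents do not settle this, and no frequency can be given.

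**The case against.** The best case against acting is that this is an editorial slip with little consequence. Section 5.1.3 presents the appendix as suggested management and Section 5.1.5 calls it guidance. Grading rests on NCI-CTCAE, so the bracketed signs may be only a summary. A reaction that seems to fit two grades is the kind of question sent to the medical monitor. The Grade 2 list has no connecting word, so it could describe several signs together, which would leave an isolated low fever at Grade 1. The intended Grade 2 limit is not stated anywhere. Late in the study few subjects can be affected: Section 6.4 limits extended access to subjects with more than 24 months of treatment and ends mapatumumab by March 2016.

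Much of this stands as a limit on size. The safeguards are real, the remaining exposure is short, and the replacement threshold needs confirmation. It does not remove the conflict:

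- Appendix 8 says its guidelines are to be applied, and Sections 5.1.3 and 5.1.5 both send sites there.
- Requiring all the Grade 2 signs at once would leave isolated urticaria or dyspnea without a grade, so the list works only as alternatives.
- The only fever limits the appendix prints are the two that coincide.
- A call to the medical monitor during a 1-hour infusion is a poor substitute for a limit that separates the grades.

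**Conclusion.** The concern holds. The printed limit assigns an isolated drug fever below 38°C to two grades with different instructions, and it leaves a small gap at 38°C and above. This is an internal inconsistency in a safety instruction that sites use. It is worth correcting, but its effect is minor: a stop of unstated length in one infusion, with the same reduced rate afterwards. The shared re-treatment rules, the Grade 3 and Grade 4 stopping rules and the efficacy analyses are not changed by it.

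The conclusion assumes that the Grade 2 signs are alternatives and that the printed symbol is what the sponsor issued. The number of subjects affected is not in the documents, and no range is offered.

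**What to change.** In Appendix 8, change the Grade 2 fever criterion from below 38°C to drug fever ≥ 38°C, after the sponsor's clinical team has confirmed that value against NCI-CTCAE 4.0. With that limit, an isolated fever below 38°C is Grade 1 only, a fever of 38°C or more is Grade 2, and a fall below 38°C becomes a usable restart condition. If the team confirms a different value, the requirement is the same: the two grades must not share a limit, and no temperature should be left unassigned.

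Send a memo with the corrected text to any site still dosing mapatumumab. If ≥ 38°C is confirmed, the edit is one character. The total cost is that edit and the memo, with no added procedure.

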I will provide copies of the protocol, any subsequent amendments and access to all information furnished by the sponsor to study personnel under my supervision. I will discuss this material with them to ensure that they are fully informed about the investigational study agent and the study protocol. I agree to conduct this clinical trial according to the protocol described herein, except when mutually agreed to in writing with the sponsor. I also agree to conduct this study in compliance with Good Clinical Practice standards as defined by the International Conference on Harmonisation (ICH) Guideline for Good Clinical Practice, all applicable national, state, and local regulations, as well as the requirements of the appropriate Institutional Review Board/Independent Ethics Committee and any other institutional requirements.

Principal Investigator:

Signature

Date

Name (please type or print)

Institution

Address

Study Synopsis

Study Number: HGS1012-C1103

Title of the Study: A Randomized, Multi-Center, Blinded, Placebo-Controlled Study of Mapatumumab ([HGS1012], a Fully-Human Monoclonal Antibody to TRAIL-R1) in Combination with Sorafenib as a First-Line Therapy in Subjects with Advanced Hepatocellular Carcinoma

Clinical Development Phase: 2

Objectives:

Primary:

- To evaluate the efficacy of mapatumumab in combination with sorafenib in subjects with advanced hepatocellular carcinoma.

Secondary:

- To evaluate the safety of the mapatumumab in combination with sorafenib in subjects with advanced hepatocellular carcinoma.
- To determine serum mapatumumab concentrations.

Diagnosis & Inclusion Criteria:

Subjects enrolled in the study must meet the following inclusion criteria:

1. Child-Pugh Class A (see [Appendix 1](#)).
2. Barcelona Clinic Liver Cancer (BCLC) advanced stage (C) hepatocellular carcinoma, or BCLC intermediate stage (B) hepatocellular carcinoma if treatment with transarterial chemoembolization is not considered appropriate (see [Appendix 2](#)).
3. Measurable disease demonstrating intratumoral arterial enhancement by contrast enhanced computerized tomography (CT), with use of multislice scanners, or contrast enhanced dynamic magnetic resonance imaging (MRI), with at least 1 tumor lesion that meets the following criteria:
 - Located in the liver.
 - Can be accurately measured in at least 1 dimension.
 - Well delineated area of viable, hypervascular (contrast enhancement in the arterial phase) tumor that is > 2 cm in the axial plane.
 - Suitable for repeat measurement.
 - Not previously treated with locoregional or systemic treatment unless the lesion shows a well-delineated area of viable (contrast enhancement in the arterial phase) tumor that is > 2 cm in the axial plane. (If the lesion is poorly demarcated or exhibits atypical enhancement as a result of the previous intervention, then it cannot be selected as a target lesion).

4. Radiologic eligibility (measurable disease) must be confirmed by the blinded, independent, central read (BICR) prior to randomization.
5. Adequate bone marrow, renal and liver function:
 - Absolute neutrophil count $\geq 1.5 \times 10^9 / \text{L}$ or $\geq 1500 / \text{mm}^3$.
 - Platelet count $\geq 50 \times 10^9 / \text{L}$ or $\geq 50,000 / \text{mm}^3$.
 - Hemoglobin $\geq 9 \text{ g/dL}$ ($\geq 5.6 \text{ mmol/L}$) without growth factor support or transfusional support.
 - Serum creatinine level $\leq 2.0 \text{ mg/dL}$ or $\leq 176.8 \text{ } \mu\text{mol/L}$.
 - Total bilirubin $< 3.0 \text{ mg/dL}$ or $< 51.3 \text{ } \mu\text{mol/L}$.
 - Aspartate transaminase (AST) and alanine transaminase (ALT) $\leq 5.0 \times$ upper limit of normal.
 - Amylase and lipase $\leq 1.5 \times$ upper limit of normal.
 - Serum albumin $\geq 2.8 \text{ g/dL}$ or $\geq 28 \text{ g/L}$.
 - International normalized ratio ≤ 1.5 .
6. Performance status of 0, 1 or 2 on the Eastern Cooperative Oncology Group (ECOG) Scale (see [Appendix 3](#)).
7. Age 18 years or older.
8. Have the ability to understand the requirements of the study, provide written informed consent (including consent for the use and disclosure of research-related health information), and comply with the study and follow-up procedures.

AM01
21Dec10

Exclusion Criteria:

Subjects will be excluded from participating in the study if they meet any of the following exclusion criteria:

1. Any co-morbid condition that in the judgment of the investigator renders the subject at high risk of treatment complications or reduces the possibility of assessing clinical effect.
2. Received prior investigational or non-investigational cytotoxic chemotherapy, hormonal therapy, biological therapy (including but not limited to monoclonal antibodies, small molecules or other immunotherapy) to treat hepatocellular carcinoma.
3. History of organ allograft.
4. Previously received mapatumumab and/or sorafenib.
5. Underwent resection, radiofrequency ablation, radiation or chemoembolization within 4 weeks before enrollment or not recovered from such treatments.
6. Need for concomitant anticancer therapy (surgery, radiation therapy, chemotherapy, immunotherapy, radiofrequency ablation) or other investigational agents during the study treatment period.
7. Major surgery (ie, the opening of a major body cavity, requiring the use of general anesthesia) within 4 weeks before enrollment; minor surgery (except for insertion of vascular access device) within 2 weeks before enrollment; or not yet recovered from the effects of the surgery.
8. Systemic steroids within 1 week before enrollment except steroids used as part of an antiemetic regimen or maintenance-dose steroids for non-cancerous disease.
9. Hepatic encephalopathy, per the investigator's evaluation.

AM02
23Feb11

10. History of clinically significant gastrointestinal bleeding requiring procedural intervention (eg, variceal banding, transjugular intrahepatic portosystemic shunt procedure, arterial embolization, topical coagulation therapy) within 4 weeks before enrollment.
11. Gastrointestinal disease resulting in an inability to take oral medication or a requirement for intravenous hyperalimentation.
12. History of any infection requiring hospitalization or intravenous antibiotics within 2 weeks before enrollment.
13. Known brain or spinal cord metastases unless adequately treated (surgery or radiotherapy) with no evidence of progression and neurologically stable off anticonvulsants and steroids.
14. Known human immunodeficiency virus infection.
15. Unstable angina, myocardial infarction, cerebrovascular accident, \geq Class II congestive heart failure according to the New York Heart Association Classification for Congestive Heart Failure (see [Appendix 4](#)) within 6 months before enrollment.
16. Cardiac arrhythmias requiring anti-arrhythmic therapy other than beta blockers or digoxin.
17. Uncontrolled hypertension (systolic blood pressure > 150 mmHg or diastolic pressure > 90 mmHg despite optimal medical management).
18. Using and unable to discontinue use of concomitant strong CYP3A4 inducers (eg, including but not limited to St. John's Wort, dexamethasone, phenytoin, carbamazepine, rifampin, rifabutin, phenobarbital).
19. Pregnant female or nursing mother. All females with an intact uterus (unless amenorrheic for the 24 months before enrollment) must have a negative serum pregnancy test at screening. All non-sterile or non-postmenopausal females must practice a medically accepted method of contraception over the course of the study and for 60 days after the last dose of study agent.
20. Males who do not agree to use effective contraception during the study and for a period of 60 days following the final dose of study agent.
21. Subject is currently enrolled in or has not yet completed at least 30 days since ending other investigational device or drug study(s) or subject is receiving other investigational agents.
22. Acute or chronic severe renal insufficiency (glomerular filtration rate < 30 mL/min/1.73 m²) or acute renal insufficiency of any severity due to the hepato-renal syndrome.
23. Hepatitis B virus DNA levels $> 2,000$ IU/mL.

Study Design and Schedule:

This is a Phase 2, multi-center, randomized, double-blind, placebo-controlled study to evaluate the efficacy and safety of mapatumumab in combination with sorafenib in subjects with advanced hepatocellular carcinoma. In addition to receiving sorafenib, subjects will be randomly assigned to 1 of 2 treatment groups in a 1:1 ratio to receive 30 mg/kg mapatumumab or placebo.

Randomization will be stratified according to BCLC advanced stage C vs BCLC intermediate stage B and ECOG performance status (0 vs 1, 2).

Approximately 100 advanced HCC subjects will be randomized/enrolled.

Study Treatment:

Mapatumumab will be supplied in open label vials and third party unblinding will be employed. The study agent will be reconstituted by the unblinded site pharmacist or unblinded designee. The unblinded site pharmacist or unblinded designee will also be the person responsible for receiving and dispensing study agent but independent of all other study activities. All other study personnel, the subject, the Sponsor will remain blinded to the study agent received. Separate monitors will be responsible for the clinical (blinded monitor) and study agent (unblinded monitor) aspects of the study.

Subjects will receive treatment every 21 days (ie, a cycle) as outlined below:

Arm A: Sorafenib 400 mg orally twice daily continuously in each cycle + placebo intravenously on Day 1 of each cycle.

Arm B: Sorafenib 400 mg orally twice daily continuously + mapatumumab (30 mg/kg) intravenously on Day 1 of each cycle.

Subjects will continue to receive study treatment(s) until radiologic disease progression or unacceptable toxicity. Subjects unable to tolerate sorafenib may continue to receive mapatumumab/placebo every 21 days until radiographic progression. Subjects unable to tolerate mapatumumab/placebo may continue to receive sorafenib until radiographic progression. All subjects will have an end of treatment visit at least 30 days after the last dose of sorafenib and/or mapatumumab/placebo whichever is later. After discontinuation of treatment, subjects will continue to be followed for radiologic disease assessments every 6 weeks, starting 6 weeks after the previous disease assessment while on treatment, until documented radiologic disease progression (if not previously documented) and then every 3 months thereafter for survival until at least 90% of the subjects have met the survival endpoint.

Disease Assessments:

Radiologic disease assessments along with assessment of alpha fetoprotein will be performed at the end of every two 21-day cycles (ie, Cycles 2, 4, 6 and every 2 cycles thereafter). The disease assessment will be performed and documented no earlier than 5 days before the start of the next cycle. Clinical responses will be evaluated according to mRECIST for HCC (see Section 6.7 and Appendix 5). The same assessment method will be used throughout the study for each subject. If disease progression is based only on new lesions or is equivocal, images will be provided to the blinded, independent, central reader (BICR) for confirmation of disease progression. Partial response (PR) and complete response (CR) will be confirmed at the next scheduled disease assessment (no fewer than 4 weeks after the initial documentation of PR or CR). All imaging scans used for disease assessments will be made available for independent radiology review by the Sponsor or designee.

Safety Assessments:

The safety of sorafenib and mapatumumab will be assessed by evaluation of the type, frequency, and severity of adverse events (ie, according to the NCI-CTCAE Version 4.0 grading) and changes in clinical laboratory tests (hematology and clinical chemistry) and immunogenicity over time. In the event that an adverse event does not have an NCI-CTCAE Version 4.0 grading, the severity grades in Section 8.6 will be used. Adverse events (including serious adverse events) will be captured from the start of study agent administration (sorafenib and/or mapatumumab/placebo) through at least 30 days following the last dose of sorafenib and/or mapatumumab/placebo, whichever is later. Laboratory assessments will be performed at screening, and during each study visit outlined in the study calendar found in Section 6.3.

The Human Genome Sciences Review Committee (HGSRC) is comprised of the Department Heads of Biostatistics, Regulatory Affairs and Drug Development. The HGSRC will review safety data after: (1) 10 subjects have completed 1 cycle; and (2) 30 subjects have completed 1 cycle. HGSRC reviews of safety data will be conducted approximately every 4 months thereafter, until 90% of subjects have reached radiologic progression. The HGSRC may conduct additional reviews at their own request and/or at the request of the Medical Monitor. The HGSRC may request the unblinding of treatment assignment for a subject and/or treatment groups. If treatment assignments are unblinded, the rationale for the unblinding will be documented.

Immunogenicity:

Blood samples for serum antibodies to mapatumumab will be obtained as outlined in Table 6-1.

Dose Modification/Delay:

Dose modifications will not be allowed for mapatumumab/placebo. Dose modifications of sorafenib for toxicity will be made according to the guidelines provided in the treatment section (Section 5.2.3) of the protocol.

Details regarding pre-treatment and management of hypersensitivity reactions related to mapatumumab are provided in Section 5.1.5 and Appendix 8.

Pharmacokinetics:

Multiple blood specimens will be obtained from subjects for serum mapatumumab concentration determinations as outlined in Table 6-1.

Pharmacodynamics:

Subjects will be given the option to participate in a biomarker research sub-study. Consenting subjects will be asked to provide a historically obtained biopsy sample, if available, and several blood samples. In addition, samples will be requested from subjects who undergo a biopsy during the treatment period.

To examine biomarkers present peripherally, blood will be drawn during Cycles 1 and 2, from which DNA and serum proteins will be isolated. The biomarker sub-study is detailed in [Appendix 6](#).

Exploratory Assessments:

Blood samples will be collected for quantification of B and T lymphocyte subsets on Day 1 (prior to dosing) and Day 15 of Cycles 1 and 2.

Study Endpoints:

The following will be evaluated (these endpoints and the respective analyses are defined in Section [9](#)):

Primary:

- Time to progression (TTP).

Secondary:

- Overall survival.
- Progression-free survival.
- Objective response (complete response [CR] + partial response [PR]).
- Disease control (CR + PR + stable disease [SD]).
- Response duration and time to response in responders.
- Frequency and severity of treatment-emergent adverse events.
- Laboratory parameters.
- Serum mapatumumab concentrations for use in a population pharmacokinetic analysis.

Statistical Methods:

Sample Size:

A total of approximately 100 subjects will be randomly assigned to 1 of 2 arms and treated with either sorafenib + placebo or the 2-agent combination of sorafenib and mapatumumab at 30 mg/kg in a 1:1 ratio. A sample size of 50 subjects randomized and treated in each group is sufficient to estimate the median time to progression with a precision of approximately -1.9 M to +2.6 M relative to the observed median. In addition, a sample size of 50 patients per arm will provide 80% power to detect an improvement in TTP from 5.5 to 8.9 M with at a one-sided significance level of 0.10.

Statistical Analysis:

The primary analysis will be an estimate of median time to progression in each arm using Kaplan Meier methods, reported with 95% confidence intervals, along with testing the hazard ratio for time to progression at a 1-sided significance level of 0.10 with a Cox

proportional hazards model controlling for the factors stratifying the randomization as covariates. Secondary analyses include estimates, using Kaplan Meier methods, of median progression-free survival (PFS) and median overall survival (OS) along with associated logrank testing. In addition, estimates of overall response rate (CR+PR) and disease control rate (CR+PR+SD) will be reported with 95% confidence intervals and an estimate of the difference in response rates and disease control rates between groups will be reported and tested for significance with a Pearson chi-square test (or Fisher's exact test). For frequency and severity of adverse events and laboratory toxicity grading, counts and rates will be presented.

Study Calendar:

The study calendar is located in Section [6.3](#) of the protocol.

Table of Contents

Study Synopsis	3
Table of Contents.....	10
List of Tables	13
List of Abbreviations	14
1 Background.....	16
1.1 Hepatocellular Carcinoma	16
1.2 Treatment Options for Patients with Hepatocellular Carcinoma.....	16
1.3 The Role of the TRAIL Pathway in HCC	16
1.3.1 TRAIL and TRAIL Receptors	16
1.3.2 TRAIL and HBV/HCV Infection	17
1.4 Mapatumumab	17
1.4.1 Mapatumumab Pharmacology	17
1.4.2 Non-Clinical Mapatumumab Safety Studies	18
1.4.3 Clinical Experience with Mapatumumab	19
1.5 Rationale for the Evaluation of Mapatumumab in Combination with Sorafenib in Hepatocellular Carcinoma	20
1.6 Rationale for Dose Selection	21
2 Study Objectives.....	22
2.1 Primary Objective.....	22
2.2 Secondary Objective.....	22
3 Study Design.....	22
3.1 Basic Design Characteristics	22
4 Inclusion and Exclusion Criteria	23
4.1 Inclusion Criteria	23
4.2 Exclusion Criteria	24
5 Study Treatment Regimen	26
5.1 Mapatumumab and Placebo.....	26
5.1.1 Formulation	26
5.1.2 Packaging, Labeling, Preparation, and Storage.....	26
5.1.3 Mapatumumab/Placebo Dose, Route of Administration and Schedule	26
5.1.4 Mapatumumab/Placebo Dose Toxicity/Delay	27
5.1.5 Management of Allergic/Hypersensitivity Reactions to Mapatumumab/Placebo	28
5.2 Sorafenib.....	28
5.2.1 Packaging, Labeling, Preparation, and Storage	28
5.2.2 Anticipated Toxicities with Sorafenib.....	28
5.2.3 Alteration of Sorafenib Dose/Schedule Due to Toxicity	29

5.3	Concurrent Medications and Therapies.....	32
5.3.1	Allowable Regimens.....	32
5.3.2	Prohibited Medications.....	32
5.3.3	Prohibited Therapies.....	32
6	Study Procedures	32
6.1	Screening Procedures	32
6.2	Study Enrollment/Randomization Procedures.....	33
